Official title: Prospective Effect of Intravenous Ketorolac on Opioid Use, EBL and Complications Following Cesarean Delivery

NCT number: NCT02509312

Document date: 2/28/2022

Basic study design:

Randomized Control Trial: Double-Blind Placebo-Controlled Trial

Study population and assembly of patients:

We will study 70 healthy (ASA 1 or 2) women between 18 and 45 years old with singleton term pregnancies undergoing or non-scheduled, non-urgent primary or repeat Cesarean delivery between 37-42 weeks gestational age with neuraxial anesthesia with combined spinal-epidural placed for surgery.

Exclusion criteria are as follows: unable or unwilling to provide informed consent, urgent or emergent Cesarean delivery, multiple fetal gestations (>1 intrauterine pregnancy), patients undergoing Cesarean delivery for bleeding such as placental abruption or actively bleeding placenta previa or vasa previa, contraindication to NSAID use eg: allergy, chronic renal disease, acute or chronic platelet dysfunction (e.g.: idiopathic thrombocytopenic purpura, HELLP syndrome), platelets <100k, history of peptic ulcer disease, inherited or acquired coagulopathies or bleeding disorder, (disseminated intravascular coagulopathy, hemophilia), suspected or proven placenta accreta, increta or percreta, inability to receive epidural morphine, patients with a diagnosed chronic pain disorder on chronic adjunct or opioid analgesia, use of general anesthesia during procedure.

Intraoperative exclusion criteria include an EBL > 1000 ml prior to cord clamp.

Randomization & Blinding:

Patients will be randomized to receive either ketorolac 30 mg in 1 ml (n=35) or normal saline 1 ml (n=35). Randomization will be performed by the Investigational Pharmacy in a block of four design. No one involved with patient care, enrollment or data collection will have access to the unblinding key until completion of the study. The randomization key will be kept in the Investigational Research Pharmacy, and they will prepare the medications accordingly. Upon arrival in the OR, the anesthesiologist will open an envelope that will contain the kit number corresponding to the patient's study identification number. The anesthesiologist or anesthetist will remove the assigned kit from the Omnicell. Patients, clinicians and study staff will be unaware of the patient's assigned study group. Upon study completion by all patients, the randomization key will be provided to the study staff upon request.

Brief Study Methods:

After obtaining written informed consent, the Investigation Research Pharmacy an envelope that will contain the kit number corresponding to the patient's study identification number. Basic demographic information is collected from the patient. Each patient will undergo combined spinal-epidural anesthesia with our standard cesarean induction dose of hyperbaric 0.75% bupivacaine 1.5 ml intrathecally and fentanyl 100mcg epidurally. The patient will be moved to the supine position with left lateral uterine displacement. When a T6 sensory level to pinprick is achieved, Cesarean delivery will proceed using the standard procedures established in our institution. Once the newborn is delivered and the cord is clamped, the first dose of the ketorolac/placebo will be administered by the anesthesiologist or anesthetist. Any additional medications required for sedation or pain control during the remainder of the surgery (hydromorphone and acetaminophen) will be given, as appropriate for patient comfort. Prior to the completion of the procedure, the patient will receive epidural morphine 3 mg per the standard protocols. Postoperatively, the patient will receive the corresponding three additional

scheduled doses of ketorolac/placebo every 6 hours. Supplemental analgesia will be administered according to a standard post-operative pain management protocol on labor and delivery with acetaminophen and intravenous hydromorphone provided, as needed for pain control.

Exposures and their measurement:

Exposure: Ketorolac 30 mg IV or Normal Saline 1 ml (Placebo) IV

Measurements: See outcomes and their measurements

Outcomes and their measurement:

Primary outcome: Estimated Blood Loss (EBL) will be compared between groups.

Secondary outcomes: Rate of Post-Partum Hemorrhage, Corrected Change in Hct on POD1, Uterotonic Doses, Units of Packed Red Blood Cell Transfused, Hydromorphone Use, Total Hydromorphone Dose, Anti-emetic Doses, Pruritus Doses, Percentile Change in Systolic Blood Pressure at 6, 12, and 24 hours, Percentile Change in Diastolic Blood Pressure at 6, 12, and 24 hours, and Pain score at 0 and 15 minutes and 1, 6, 12 and 24 Hours post-Cesarean Delivery.

Confounders and their measurement:

Many confounders should be limited by the nature of an RCT in a select patient population and pre- and intra-operative exclusion criteria. Additional potential confounders, including intraoperative fluid volume administration and patient adherence to study medication, will be recorded. Posthoc analysis will be performed to determine if any differences between groups were significant.

Analysis plan:

Data will be assessed for normality using histograms, QQ plots and Shapiro-Wilk test. Demographic, obstetric, and perioperative data will be presented as mean (standard deviation), median [interquartile range] or count (percentage), as appropriate. Between-group comparisons will be assessed using the t-test and Wilcoxon signed-rank test, as appropriate. For dichotomized outcomes, a Chi-square test will be performed to assess the proportions between groups.

Sample size justification:

A priori power analysis was performed to determine the sample size. Based on our prior retrospective study, we knew that the mean estimated blood loss for uncomplicated Cesarean deliveries was 814 ml with a standard deviation of 242 ml. We set our difference between groups to 186 ml. This would detect an EBL of >1,000 ml in the ketorolac group, a value large enough to classify the ketorolac group as post-partum hemorrhage and potentially escalate care and lead to additional maternal morbidity. With an alpha error of 0.05 and a power of 80%, we estimated that a sample size of 28 patients per group would be needed or 56 total patients enrolled. We had concern for loss after enrollment due to acuity, cases after 4 pm and exclusion criteria including intraoperative EBL and obstetric refusal. We planned for the loss of 20% of enrolled patients and increased the total study enrollment number to 70.

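### Blood loss before cord clamp precedes the first dose but is not named as a covariate; adjusting the primary EBL comparison for it would be a cheap gain in precision

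*Combined protocol and SAP*

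**What the plan says.** The outcome section defines the primary endpoint in one line: "Primary outcome: Estimated Blood Loss (EBL) will be compared between groups". It gives no start or end for the measurement window.

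Brief Study Methods fixes when treatment begins: "Once the newborn is delivered and the cord is clamped, the first dose of the ketorolac/placebo will be administered". The study population section sets a threshold on loss before that moment: "Intraoperative exclusion criteria include an EBL > 1000 ml prior to cord clamp".

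The confounder section opens with "Many confounders should be limited by the nature of an RCT in a select patient population and pre- and intra-operative exclusion criteria". It then names two further variables: "Additional potential confounders, including intraoperative fluid volume administration and patient adherence to study medication, will be recorded". It plans a post hoc look at whether the groups differ, but no adjusted model.

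The analysis plan is unadjusted: "Between-group comparisons will be assessed using the t-test and Wilcoxon signed-rank test, as appropriate". The sample size rests on a "mean estimated blood loss for uncomplicated Cesarean deliveries was 814 ml with a standard deviation of 242 ml", a target difference of 186 ml, alpha 0.05, 80% power, 28 per group, and 70 enrolled after allowing for 20% loss. The reasons given for that loss include "exclusion criteria including intraoperative EBL and obstetric refusal".

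**The concern.** Blood lost before the cord is clamped cannot be an effect of ketorolac, because no study drug has been given. If that blood is part of the primary EBL, it adds variation that carries no information about treatment. The plan already needs someone to judge the quantity, but uses it only as a cut-off.

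The cut-off removes little of that variation. Under a normal distribution with mean 814 ml and SD 242 ml, about 22% of deliveries exceed 1000 ml in total. If those figures describe total loss, no larger share can exceed 1000 ml before clamp.

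The two variables that are named do not fill the gap. Adherence arises from dosing onward. Total intraoperative fluid volume mixes fluid given before and after the first dose. Neither is a clean pre-dose measure of bleeding.

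What is at stake is precision in a trial sized to detect a bleeding harm with just over 80% power. A wide interval around a non-significant difference gives weak reassurance.

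**Working it through.** **Inputs from the Sample size justification:** SD 242 ml, difference 186 ml, alpha 0.05 (two-sided, because a one-sided test needs only 21 per arm and does not match), 28 per arm.

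**Assumed, because the documents give no figure:** the share R² of EBL variance explained by pre-clamp loss, taken as 10%, 30% and 50%; pre-clamp loss independent of later loss; EBL equal to total procedural loss.

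**1. The plan's own figure.** The standard error of the difference is 242 × √(2/28) = 64.7 ml. The noncentrality is 186/64.7 = 2.88 on 54 df, which gives 80.6% power. With 27 per arm power is 79.2%, so 28 is the smallest adequate number. Then 56/0.80 = 70. Both stated figures reproduce.

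**2. Adjusted analysis.** The residual SD is 242 × √(1 − R²), with 53 df.

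| R² | Residual SD (ml) | Power, 186 ml | Difference detectable at 80% power (ml) | 95% CI half-width (ml) |
|---|---|---|---|---|
| Unadjusted | 242 | 80.6% | 185 | 130 |
| 0.10 | 230 | 84.5% | 175 | 123 |
| 0.30 | 202 | 92.1% | 154 | 109 |
| 0.50 | 171 | 97.9% | 131 | 92 |

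Simulation of 20,000 trials per setting under normal errors gave 83.9%, 91.8% and 97.9% power, with a mean adjusted estimate of 186 to 187 ml. With no true effect, the adjusted type I error was 0.048 to 0.054. Adjustment therefore does not distort the estimate or the test.

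**3. Chance imbalance.** The standard error of the between-arm difference in mean pre-clamp loss is 242 × √R² × √(2/28) = 20.5, 35.4 and 45.7 ml. Multiplied by 1.96, this is ±40, ±69 and ±90 ml. It is not additional to the planned interval. At R² = 0.30, for example, the residual standard error is 202.5 × √(2/28) = 54.1 ml, and √(35.4² + 54.1²) = 64.7 ml, the unadjusted standard error from step 1.

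**4. Less favourable cases.**
- Crude cord-clamp estimate (error SD equal to the true spread, rounded to 100 ml): power of about 82%, 86% and 90%.
- Covariate that explains nothing: 79% to 80% in simulation, a loss of about one percentage point.
- Primary EBL counting only post-clamp loss: no gain under the independence assumption, because the pre-clamp component is not in the outcome.

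**The case against.** The strongest reply is that nothing is wrong with the planned test. Randomisation makes the unadjusted comparison valid. If 242 ml is the SD of total EBL, the sample size already allows for pre-clamp variation, and the trial reaches the power it states. This stands in full.

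A reader might infer that imbalance in pre-dose bleeding would bias the result, or be mistaken for a drug effect outside the stated uncertainty. The documents do not support that: as step 3 shows, the imbalance is one component of the roughly ±130 ml interval.

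A reader might also infer that the plan relies on exclusions alone, or that it could never reveal a difference in pre-clamp loss. That goes too far. The confounder section names the randomised design as well as the exclusions. Its list is open-ended, and perioperative data are to be presented and groups compared. Pre-clamp EBL is simply not named.

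Nor is the right contrast before versus after allocation. The kit envelope is opened on arrival in the OR, so pre-clamp loss also follows allocation. It is an acceptable covariate because it precedes the first dose and staff are blinded.

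Finally, judging loss against a threshold does not prove that a usable number exists, and the size of the gain is unknown. Both points stand, and they limit how strongly the change can be urged.

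**Conclusion.** The point holds as a specific, low-cost improvement. It is not a defect in the planned test, which is valid and delivers 80.6% power at 28 per arm. Adjusting for pre-clamp EBL would raise that to about 84%, 92% or 98% if it explains 10%, 30% or 50% of the variance, and would narrow the 95% half-width from 130 ml to 123, 109 or 92 ml.

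These gains rest on two things the documents do not settle. One is the variance share, which is assumed. The other is that primary EBL includes pre-clamp loss. The 814 ml mean for Cesarean deliveries and the use of 1,000 ml as the hemorrhage line make that the likelier reading, but the window is not defined. A crude estimate shrinks the gain, and an uninformative one costs about one percentage point of power.

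Calling fluid volume and adherence confounders is a wording matter, since the planned EBL test does not adjust for them.

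**What to change.** - State that primary EBL includes loss before cord clamp.
- Record the EBL judged at cord clamp as a number for every patient, while staff are blinded, and report it by arm.
- Prespecify the primary comparison as ANCOVA with terms for arm and pre-clamp EBL, on the ml scale on which the 186 ml target is set. Do not add a transformation or rank fallback chosen from the data. Keep the unadjusted test as a sensitivity analysis.
- Report fluid volume and adherence by arm as descriptions of what happened after allocation. Do not adjust for them or exclude patients on them in the primary comparison.

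The cost is one number per patient, one residual degree of freedom and a few lines of SAP text. Part of the Sample size justification is in the past tense, so data may already exist. If they were collected without the cord-clamp value, the adjustment is unavailable. What remains is to define the EBL window and settle how fluid volume and adherence are described and used.

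### The plan names the Wilcoxon signed-rank test, a paired test, for comparing two independent randomised arms, and the primary outcome can be sent to it

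*Combined protocol and SAP*

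**What the plan says.** The Analysis plan first sets a normality check: "Data will be assessed for normality using histograms, QQ plots and Shapiro-Wilk test". It then assigns the tests: "Between-group comparisons will be assessed using the t-test and Wilcoxon signed-rank test, as appropriate". Dichotomous outcomes go to a chi-square test. No rank-sum or Mann-Whitney test is named anywhere, and the signed-rank test is not limited to changes within a patient.

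The design is a parallel two-arm trial. Under Randomization & Blinding: "Patients will be randomized to receive either ketorolac 30 mg in 1 ml (n=35) or normal saline 1 ml (n=35"; and "Randomization will be performed by the Investigational Pharmacy in a block of four design". Under Outcomes and their measurement: "Primary outcome: Estimated Blood Loss (EBL) will be compared between groups". The Sample size justification is built on a difference in mean EBL: "We set our difference between groups to 186 ml".

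**The concern.** The signed-rank test takes one difference per pair and ranks those differences. It needs the same number of observations on each side and a real link between the members of each pair. Blocked randomisation to two arms supplies neither, because a block of four does not create matched pairs of patients.

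Three things follow. With unequal arms the test cannot be run. With equal arms someone must invent a pairing, usually the order of rows in the data file, and the p-value changes with it. Some power is also lost against the test that fits the design.

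The outcomes most likely to take the non-parametric branch are uterotonic, anti-emetic and pruritus doses, units transfused, total hydromorphone dose and pain scores. The documents give no distributions for these, but counts with many zeros and bounded scores are plausible. EBL is exposed too, because its test is left to the normality check although the sample size rests on a difference in means.

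**Working it through.** **1. Inputs.** From the Sample size justification: mean 814 ml, SD 242 ml, difference 186 ml, alpha 0.05, power 80%, 28 per group, 20% loss, 70 enrolled. From Randomization & Blinding: 35 v 35. The shape of the EBL distribution is not given, so every shape below is an assumption.

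**2. The plan's own sample size.** The normal approximation for two independent means is n = 2(1.960 + 0.842)² × (242/186)² = 2 × 7.85 × 1.693 = 26.6, so 27 per arm. The independent two-sample t-test (noncentral t, two-sided) gives 27.57, so 28 per arm, with power 80.6% at 28. Allowing for loss: 56/0.80 = 70. The stated figures are reproduced. A one-sided test would give 21 per arm by the normal approximation and does not match. The plan's power calculation therefore treats the arms as independent, while its non-parametric test treats them as paired.

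**3. Can the test be computed?** Suppose exactly 14 of 70 are lost at random from arms of 35. Then P(equal arms) = C(35,7)²/C(70,14) = 0.234, so P(unequal) = 0.766. If blocks of four are simulated without forcing 35/35, P(unequal) is 0.776. If each patient is lost independently with probability 0.20, it is about 0.88. Given arms of 27 and 29, the software returned an error.

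**4. How often would EBL be sent to it?** Take Shapiro-Wilk p < 0.05 as the switch. This is a simplification, since the plan also uses plots and states no threshold. With mean 814 and SD 242 the coefficient of variation is 242/814 = 0.297, and a lognormal has skewness 3(0.297) + 0.297³ = 0.92.

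| Assumed shape | Rejection, pooled n = 56 | Rejection in either arm of 28 |
|---|---|---|
| Normal | about 5% | about 10% |
| Gamma | about 33% | about 33% |
| Lognormal | 59% | 54–55% |

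**5. If the arms are equal, is the answer stable?** Lognormal data sets of 28 v 28 were simulated and one arm was re-paired at random thousands of times. In data sets with a rank-sum p of about 0.03, the signed-rank p ran from about 0.001 up to between 0.16 and 0.21. The share of pairings with p ≥ 0.05 varied by data set, from 15% to 36%. In another data set, with a rank-sum p of 0.58, the signed-rank p ran from 0.08 to 1.00. These illustrate dependence on row order; they are not error rates.

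**6. Type I error and power at 28 per arm** (10,000 simulated trials per row; arbitrary pairing for signed-rank; a location shift of 186 ml for power):

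| Shape | Signed-rank type I error | t-test power | Rank-sum power | Signed-rank power |
|---|---|---|---|---|
| Normal | 4.6% | 80.9% | 78.1% | 77.0% |
| Lognormal | 4.5% | 80.4% | 83.4% | 79.5% |
| More skewed (skewness about 2) | 4.8% | 80.7% | 93.4% | 85.7% |

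**7. Does the correction change the sample size?** Under normality the rank-sum test has relative efficiency 3/π = 0.955, so sizing on it gives 27.57/0.955 = 28.9, or 29 per arm. Enrolment would be 58/0.80 = 72.5, or 73. At the lower bound for efficiency, 0.864, it is 27.57/0.864 = 31.9, or 32 per arm and 64/0.80 = 80 enrolled. If the t-test is primary for EBL, 28 per arm stands as calculated.

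**The case against.** The strongest reply is that this is a naming slip. The sentence concerns comparisons between groups, and the sample size reproduces only as an independent two-sample calculation, so the authors evidently understood the arms to be independent. Because the signed-rank test fails on unequal arms, the mistake would often be noticed before it produced a result. A slip is plausible. Even so, the written plan names the paired test, and an analyst must either follow it or depart from it without a pre-specified basis.

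The test also does not inflate type I error under arbitrary pairing. That is correct. It is wrong here because it is not defined for unpaired arms and its result cannot be reproduced, not because it rejects too often.

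The effect on EBL is conditional. If EBL looks normal, the t-test applies. The exposure depends on an assumed shape, and excluding patients who lose more than 1000 ml before cord clamping may trim the upper tail. This stands, and it is why a range is shown instead of a single figure.

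Finally, choosing the test by a normality check is a separate and milder matter. Once rank-sum replaces signed-rank, either branch performs acceptably at 28 per arm. Fixing one primary test is sound practice but is not needed to cure the error.

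**Conclusion.** The concern holds. As written, the non-parametric test does not fit the design for any between-group comparison. With 14 random losses from 35 v 35 it could not be computed in 77% of trials (about 88% if losses are independent at 20%). Where it could be computed, arbitrary row order could decide significance for a borderline result.

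The chance that the primary outcome meets this test is roughly 5% to 60%, depending on the assumed shape of EBL and on reading Shapiro-Wilk at 5% as the switch. The loss of power against rank-sum is about 1 point for normal data, 4 for lognormal and 8 for the more skewed shape. The false-positive rate is not raised, and the stated sample size is not in error on this point. The error must be corrected because it is in the main analysis sentence and can reach the primary outcome.

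**What to change.** **Required.** In the Analysis plan, replace the signed-rank test with the Wilcoxon rank-sum (Mann-Whitney U) test for all between-group comparisons of continuous, count and ordinal outcomes. This includes changes in hematocrit and blood pressure when these are compared between arms.

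**Recommended, and secondary.** Name the primary test for EBL in advance and do not let Shapiro-Wilk choose it. A Welch t-test on the difference in means matches the basis of the sample size. Report the rank-sum test with the Hodges-Lehmann difference as a sensitivity analysis.

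**Cost.** One phrase for the required change and one or two sentences for the rest. No further patients or data are needed, and 28 per group (70 enrolled) can stand.

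### Blood pressure (secondary outcomes) is compared as unadjusted percent change; adding the baseline reading as a covariate would usually give more precision from the same data

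*Combined protocol and SAP*

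**What the plan says.** Outcomes and their measurement lists, among the secondary outcomes, "Percentile Change in Systolic Blood Pressure at 6, 12, and 24 hours" and "Percentile Change in Diastolic Blood Pressure at 6, 12, and 24 hours", which makes six comparisons, and "Corrected Change in Hct on POD1". It does not say which reading is the baseline for pressure or how the haematocrit change is corrected. 'Percentile' is not explained; percent change from baseline is the natural reading.

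The Analysis plan then says: "Between-group comparisons will be assessed using the t-test and Wilcoxon signed-rank test, as appropriate". Dichotomised outcomes get a chi-square test. No regression model or baseline term appears, and no confidence intervals are promised.

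The only further analysis is under Confounders and their measurement: "Additional potential confounders, including intraoperative fluid volume administration and patient adherence to study medication, will be recorded", followed by "Posthoc analysis will be performed to determine if any differences between groups were significant". Baseline values of the outcomes are not among the variables named there.

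**The concern.** A percent change cannot be formed without a baseline value, so the trial already holds the most useful covariate for each blood pressure outcome. Percent change uses it with a fixed weight: in effect it subtracts the baseline multiplied by the ratio of the follow-up mean to the baseline mean, whatever the data show. A linear model estimates that weight. When the true slope of follow-up on baseline is smaller than the ratio of the means, the fixed weight over-corrects and adds noise.

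What is at stake is precision on secondary outcomes in a trial that expects about 56 analysed patients and was sized for EBL alone. Because the plan promises tests and not intervals, the loss would show as lower power or, if intervals are reported, as wider ones.

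**Working it through.** **The plan's own figure.** Sample size justification gives "the mean estimated blood loss for uncomplicated Cesarean deliveries was 814 ml with a standard deviation of 242 ml", a difference of 186 ml, alpha 0.05 and power 80%. Taken as two-sided, the normal approximation is 2 × (1.96 + 0.842)² × (242/186)² = 26.6, so 27 per group. The exact t-test gives 28 per group (power 80.6%; 27 gives 79.1%). Then 56/(1 − 0.20) = 70. The stated numbers reproduce, and nothing below alters them.

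**Inputs for blood pressure.** The documents give none, so all of these are assumptions: systolic baseline mean 120, SD 14; diastolic mean 70, SD 10; correlation ρ from 0.3 to 0.7; ratio of follow-up mean to baseline mean m = 1 or 0.9; ratio of follow-up SD to baseline SD k = 1, then 0.8 to 1.3. The number analysed, 56, is the plan's.

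**Formula.** To first order, the variance of percent change (rescaled to mmHg) relative to the baseline-adjusted model is

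R = 1 + (m − ρk)² / [k²(1 − ρ²)].

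Here ρk is the slope of follow-up on baseline, so R = 1 when the slope equals m. Estimating one slope costs a factor 1 + 1/(56 − 4) = 1.019, and the net ratio is R/1.019. It is read as the multiple of patients that percent change needs.

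**Equal SDs (k = 1).** With m = 1 and ρ = 0.3, R = 1 + 0.49/0.91 = 1.54. Simulation with 4 million draws gives 1.60 for systolic pressure; the excess arises because dividing by a varying baseline adds noise that the first-order formula ignores. Simulated net ratios:

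| | ρ = 0.3 | ρ = 0.5 | ρ = 0.7 |
|---|---|---|---|
| Systolic, m = 1 | 1.57 | 1.35 | 1.18 |
| Systolic, m = 0.9 | 1.42 | 1.22 | 1.08 |
| Diastolic, m = 1 | 1.61 | 1.38 | 1.20 |
| Diastolic, m = 0.9 | 1.45 | 1.25 | 1.09 |

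Intervals would be wider by the square root: √1.08 = 1.04 up to √1.61 = 1.27. Equivalently, 56 patients compared by percent change give the precision of about 56/1.61 = 35 to 56/1.08 = 52 compared with adjustment. At ρ = 0.9 the gross systolic ratios are 1.073 (m = 1) and 1.015 (m = 0.9). Divided by 1.019 they are 1.05 and 0.996, so the gain is almost nil.

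**Unequal SDs.**
- k = 0.8, m = 1, ρ = 0.3: R = 1 + (1 − 0.24)²/(0.64 × 0.91) = 1 + 0.5776/0.5824 = 1.99. Simulated net ratio about 2.1 for both pressures.
- k = 1.3, m = 0.9, ρ = 0.7: the slope is 0.91, almost equal to m, so R = 1 + 0.0001/0.862 = 1.00. Simulated net ratio about 1.00, no gain.

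Over k of about 0.8 to 1.3 and ρ of 0.3 to 0.7, the range is therefore about 1.0 to 2.1.

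**Error rate.** Simulated trials at 28 per arm with equal SDs gave a type I error of 4.8 to 5.2% for both the t-test on percent change and the adjusted model.

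**Keeping percent change as the outcome.** With baseline added as a covariate to percent change, the variance is within about 2 to 5% (at most 8%) of that of the model for the follow-up value, so almost all of the gain is kept.

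**Haematocrit.** The correction is undefined, so no ratio can be computed.

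**The case against.** The strongest case against is that this is a choice and not a fault. Comparing percent change in a short plan is conventional, the outcomes are secondary, and no power is promised for them. Every blood pressure input is assumed. The size also depends on the SD ratio as well as the correlation. Combined spinal-epidural anaesthesia precedes the first dose and the baseline reading is not named, so equal SDs cannot be presumed. All of this stands. It limits the point to an optional improvement and means that 1.08 is not a floor: the gain can be nil.

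Four stronger readings are tempting and not supported:
- *That the unadjusted analysis is biased.* Randomisation makes the two-sample t-test on percent change unbiased.
- *That the whole quoted sentence is therefore sound.* It names the Wilcoxon signed-rank test, a paired test, for two independent groups. That is a separate error, and no validity is claimed for it here. The ratios above compare with the t-test only.
- *That percent change is worse than ignoring baseline.* To first order this requires ρ < m/(2k). Over the ranges used, that threshold runs from 0.9/2.6 = 0.35 to 1/1.6 = 0.63, and the documents give no correlation.
- *That EBL needs an adjusted model or a new sample size.* EBL has no pre-treatment value, and the stated N reproduces.

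A further objection is that modelling mmHg changes the outcome's scale. That is fair, and the second option in the fix avoids it.

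**Conclusion.** The point holds as an optional improvement at almost no cost, for secondary outcomes only. Adjusting each blood pressure outcome for a baseline that the trial must already hold would usually improve precision. On assumed values, percent change needs about 1.08 to 1.6 times the patients with equal SDs and correlation 0.3 to 0.7, and about 1.0 to 2.1 times once the SD ratio may range from about 0.8 to 1.3. The gain vanishes when the slope of follow-up on baseline is close to the ratio of the means; the worst-case loss is then about 2% of variance. For haematocrit the point applies in form only.

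**What to change.** Before unblinding, add to the Analysis plan:

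1. For systolic and diastolic pressure at each of 6, 12 and 24 hours, a linear model of the follow-up value on treatment and baseline. Report the adjusted difference in mmHg with a 95% CI, and keep percent change as a descriptive summary. Alternatively, keep percent change as the outcome and add baseline as the covariate.
2. The pre-dose reading that serves as baseline, and 'percent' in place of 'percentile'.
3. A statement that intraoperative fluid volume and adherence do not enter these models. Adherence is observed after the first dose, and fluid may still be given after it, so neither is a pre-dose variable.
4. For haematocrit, the definition of the correction, with pre-dose haematocrit as a covariate for the planned corrected change.

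The cost is SAP wording and one degree of freedom per model. No new data item, patient or procedure is needed. Under the first option in item 1, the tested difference is in mmHg instead of percent. Fixing the model before the key is released matters because the open-ended post hoc clause would otherwise leave the choice of model until the results are known.
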